### 10.4. Outcome Measures Related to Neurocognitive Assessment Analysis

The cognitive tests administered include computerized tests from the  Battery and traditional neurocognitive instruments.

#### **Bayley Scales of Infant and Toddler Development – Third Edition (Bayley-III; Neurodevelopment)**

Bayley Scales of Infant and Toddler Development – Third Edition (Bayley-III) is a revision of the Second Edition (BSID-II), but while the prior provided mental, motor and behavioral scales, the psychologist-administered Bayley-III provides cognitive, language, motor, social-emotional, and adaptive behavioral scales. To avoid duplication in domains, the adaptive behavioral scale of Bayley-III will not be performed as it is identical to the Adaptive Behavioral Assessment System, 2nd edition (ABAS-2), and ABAS-3 is already being used in this study.

- Bayley III (ages 1:0 to 3:6 years), excluding ABAS-2 domain test

Primary scales of intelligence have continued to be an integral part of assessment of neurocognitive function.

Assessment of intelligence across multiple domains is different in the pre-school setting from that of older children and adults.

#### **Wechsler Preschool and Primary Scale of Intelligence – Fourth Edition (WPPSI-IV; General Intelligence)**

The Wechsler Preschool and Primary Scale of Intelligence – Fourth Edition (WPPSI-IV) is the latest edition of the individually administered early childhood intelligence test with origins dating back to the original 1967 Wechsler Preschool and Primary Scale of Intelligence. The WPPSI-IV is divided into two distinct age bands (2 years 6 months to 3 years 11 months and 4 years 0 months to developmental changes during the age range covered. Only the latter will be used in this study due 7 years 7 months) corresponding to different subtest batteries due to significant cognitive ability and to overlap with Bayley-III in infants. Six of the WPPSI-IV subtests will be completed in this study: 3 subtests to align to WASI-II (Block Design, Matrix Reasoning, Similarities) and 5 partially overlapping subtests required to generate a composite or full scale IQ (Matrix Reasoning, Information, Similarities, Picture Memory, Bug Search); Matrix Reasoning also provides a proxy for non-verbal IQ.

- WPPSI-IV 4:0-7:7 (ages 4:0-6:11 years)
  - Block Design
  - Matrix Reasoning
  - Similarities
  - Information

- Picture Memory
- Bug Search

### **Wechsler Abbreviated Scale of Intelligence – Second Edition (WASI-II; General Intelligence)**

The Wechsler Abbreviated Scale of Intelligence – Second Edition (WASI-II) is an abbreviated measure of intelligence designed for individuals 6 to 90 years of age. Primarily used in clinical, psychoeducational, and research settings, the WASI-II was developed to quickly and accurately estimate intelligence when administration of a full battery is not feasible or necessary. The WASI-II is classified as a Level C measure, and can be administered and interpreted by individuals with a doctorate degree in psychology or a related discipline. Administration time is approximately 30 min for the four-subtest form.

- WASI-II (ages 7-21)

### **Behavior Assessment System for Children (BASC; Behavior/Emotion)**

Behavioral assessment is multidimensional, including adaptive and problem behavior to identify emotional and behavioral problems. It typically includes a combination of assessment in various or school setting, and through self-report of older children and adolescents to identify their thoughts settings, through parents to assess the home or community, through teachers to assess the preschool and feelings. The Behavioral Assessment System for Children (BASC) was developed in 1992 as a multidimensional assessment including Structured Developmental History (SDH), Parent Rating Scale (PRS), Teacher Rating Scale (TRS), Self-Report of Personality (SRP) and Student Observation System (SOS), which can be used separately or in combination. The current third edition, BASC-3, provides a comprehensive set of rating scales that measure areas important for IDEA and DSM-5 classifications. In this cross-sectional study, the parent rating scale (PRS) and self-report of personality (SRP) will be utilized.

- BASC3 Parent response scale Preschool (PRS-P 2-5y) (ages 24 months-5 years)
- BASC3 Parent response scale Child (PRS-C 6-11y) (ages 6-11 years)
- BASC3 Parent response scale Adolescent (PRS-A 12-21y) (ages 12-21)
- BASC3 Self-Reported Personality Child (SRP-C 8-11y) (ages 8-11)
- BASC3 Self-Reported Personality Adolescent (SRP-A 12-21y) (ages 12-17)
- BASC3 Self-Reported Personality College (SRP-College 18-25y) (age 18-21)

### **Adaptive Behavior System – Third Edition (ABAS-3; Adaptive Behavior)**

Adaptive behavior refers to “the level of everyday performance of tasks that is required for a person to fulfill typical roles in society, including maintaining independence and meeting cultural expectations regarding personal and social responsibility”. Measurements of adaptive behavior have been utilized by school psychologists and other mental health professionals as part of assessment/diagnosis, evaluation of behavioral conditions, and one of five domains that are a basis for eligibility for special education, is recommended in guidelines by the American Association on Intellectual and Developmental Disabilities and by the Diagnostic and Statistical Manual of Mental Disorders (DSM-5). Measures of adaptive behavior are impaired in autism spectrum disorders and attention deficit hyperactivity disorder. Adaptive behavior scales typically use semi-structured interview forms and are typically completed by parents, teachers, and other caregivers familiar with the child or adolescent and their behavior.

Evidence based reviews suggest that adaptive behavioral assessments should be part of a comprehensive assessment of children and adolescents. In this study, the Adaptive Behavior Assessment System – Third Edition (ABAS-3) scale focused on home and community setting will be used.

- ABAS-3 Parent 0-5y (ages 12 months to 5 years)
- ABAS-3 Parent 5-21y (ages 6-21)

- ABAS-3 Adult 16-89y (ages 16-21)

### **Behavior Rating Inventory of Executive Function (BRIEF; Executive Function)**

Self-regulation skills have pervasive and long-lasting implications for the development of children's academic abilities and psychopathology, and is most associated with the construct of executive function. Executive Function is characterized by three intercorrelated factors: inhibitory control, working memory, and shifting. Inhibitory control (IC) is defined as the ability to inhibit a prepotent response in favor of a subordinate response. Working memory (WM) is defined as the ability to maintain, update, and manipulate information within memory. Shifting (SH) is defined as the ability to switch attention between mental sets or tasks, or the ability to engage and disengage with specific aspects within tasks. Rating scales involving either self-report or parent and teacher reports of EF skills in everyday situations have been developed. The Behavior Rating Inventory of Executive Function (BRIEF) is a parent- or teacher-rating scale of everyday EF behaviors in school-age children. The second edition BRIEF2 was designed and modified to be used in conjunction with performance-based measures to allow for a comprehensive understanding of children's EF skills. Modified from BRIEF to address preschool issues, Behavior Rating Inventory of Executive Function – Preschool version (BRIEF-P), is intended to be completed by teachers or parents of 2- to 6-year old children, with ratings based on the child's observed behaviors within the relevant home or school environments. Behavior Rating Inventory of Executive Function – Adult version (BRIEF-A) is modified from BRIEF to address issues in adults aged 18-90 years old. In this study, parent ratings will be captured for ages 2-18 (BRIEF-P and BRIEF2) and self-report of adolescents and adults (ages 11-21, BRIEF2 and BRIEF-A).

- BRIEF-P (Preschool) Parent 2:0-5:11y (ages 24 months to 5 years)
- BRIEF2 Parent 5-18y (ages 6-18 years)
- BRIEF2 Self Report 11-18y (ages 11-18 years)
- BRIEF-A Self Report 18-90y (ages 18-21)

[figure not shown]
### **Custom Battery (DET, IDN, ONB; Attention/Processing Speed)**

Clinical assessment of attention usually depends on three sources of information: (1) psychometric tests designed to measure other cognitive functions, (2) specific neuropsychological tests of attention; and direct behavioral observation and measurement. Assessment often requires the clinician to obtain information about performance under different conditions. Measures of attention include attention span, divided attention, switching, response intention and planning, sustained performance and vigilance, and information-processing speed.

Information processing speed along with working memory have been identified as measures of cognitive impairment. While traditionally clinicians assessed with the Paced Auditory Serial Addition Test (PASAT), over the past decade the advent of computerized tests of information processing have been relied on to assess processing speed. The [REDACTED] computerized cognitive test battery proposed for this study includes an assessment of processing speed, attention/vigilance, and working memory.

- [REDACTED] Custom Battery (Peds platform, ages 4-9; Adult platform, ages 10-21)
  - Detection test (processing speed, psychomotor function)
  - Identification test (attention/vigilance)
  - One Back Test (working memory)

*Note: Ages 4-5 years old will be administered with pediatric Detection and Identification. Ages 6-9 years old will be administered with pediatric Detection, Identification, and One Back. Ages 10-21 will be administered with adult Detection, Identification, and One Back.*

Although each of the [REDACTED] computerized cognitive tests yields multiple outcome measures, research by [REDACTED] has identified a set of measures that are optimal for the detection of cognitive change in clinical trials at both the group and individual level (Falleti et al., 2006; Maruff et al., 2009; Bland & Altman, 1996a; Bland & Altman, 1996b).

For each [REDACTED] computerized cognitive test, a single primary outcome measure was selected prior to data analysis from each test in the battery to minimize experiment-wise error rates. Each primary outcome measure was selected because it has been shown to be optimal for the detection of change because:

- a) It is drawn from a data distribution that contains only a small probability of floor or ceiling effects and no restriction in the range of possible performance values (Falleti et al., 2006; Bland & Altman, 1996a; Bland & Altman, 1996b).
- b) It is drawn from a normal distribution or a distribution which can be corrected to normal through the use of appropriate mathematical transformation (e.g., logarithmic base 10, or arcsine) (Falleti et al., 2006; Bland & Altman, 1996a; Bland & Altman, 1996b).

[figure not shown]
Table 2 below summarizes the outcome measures for the neurocognitive assessments with the instruments from which they were derived.

**Table 2: Neurocognitive Instruments Administered in Study NN7999-3895 and their Primary, Secondary, and Exploratory Outcome Measures**

Primary Outcome Measure	Secondary Outcome Measure	Exploratory Outcomes
BAYLEY-III		
Cognition Composite	Receptive communication	
Communication Composite	Expressive communication	
Motor Composite	Fine Motor	
Social-Emotional Composite	Gross Motor	
WPPSI-IV		
Full-Scale IQ	Block Design subtest	
Verbal Comprehension Index	Matrix Reasoning subtest	
	Similarities subtest	
	Information subtest	
	Picture Memory subtest	
	Bug Search subtest	
WASI-II		
Full-Scale IQ	Vocabulary subtest	
Verbal Comprehension Index	Similarities subtest	
Perceptual Reasoning Index	Matrix Reasoning subtest	
	Block Design subtest	
BRIEF-P		
Global Executive Composite Index	Inhibit Scale	
Inhibitory Self-Control Index	Emotional Control Scale	
Flexibility Index	Shift Scale	
Emergent Metacognition Index	Working Memory Scale	
	Plan/Organize Scale	
BRIEF-2 Parent Report		

Global Executive Composite Index Behavioral Regulation Index Emotion Regulation Index Cognitive Regulation Index	Inhibit Scale Self-Monitor Scale Emotional Control Scale Shift Scale Initiate Scale Working Memory Scale Plan/Organization Scale Organization of Materials Scale Task Monitor Scale	
BRIEF-2 Self Report		
Global Executive Composite Index Behavioral Regulation Index Emotion Regulation Index Cognitive Regulation Index	Inhibit Scale Self-Monitor Scale Emotional Control Scale Shift Scale Working Memory Scale Plan/Organization Scale Task Completion Scale	
BRIEF-A		
Global Executive Composite Index Behavioral Regulation Index Metacognitive Index	Inhibit Scale Self-Monitor Scale Emotional Control Scale Shift Scale Initiate Scale Working Memory Scale Plan/Organization Scale Organization of Materials Scale Task Monitor Scale	
BASC3 Parent Rating Scale Preschool (PRS-P)		
Externalizing Problems Composite Internalizing Problems Composite Behavioral Symptoms Index	Hyperactivity Domain  Aggression Domain  Anxiety Domain  Depression Domain  Somatization Domain  Attention Problems Domain 	Atypicality Domain  Withdrawal Domain  Adaptive Skills Composite  Adaptability Domain  Social Skills Domain  Activities of Daily Living Domain  Functional Communication Domain 
BASC3 Parent Rating Scale Child (PRS-C)		
Externalizing Problems Composite Internalizing Problems Composite Behavioral Symptoms Index	Hyperactivity Domain  Aggression Domain  Conduct Problems Domain  Anxiety Domain  Depression Domain  Somatization Domain  Attention Problems Domain 	Atypicality Domain  Withdrawal Domain  Adaptive Skills Composite  Adaptability Domain  Social Skills Domain  Activities of Daily Living Domain  Functional Communication Domain  Leadership Domain 
BASC3 Parent Rating Scale Adolescent (PRS-A)		
Externalizing Problems Composite Internalizing Problems Composite Behavioral Symptoms Index	Hyperactivity Domain  Aggression Domain  Conduct Problems Domain  Anxiety Domain  Depression Domain  Somatization Domain  Attention Problems Domain 	Atypicality Domain  Withdrawal Domain  Adaptive Skills Composite  Adaptability Domain  Social Skills Domain  Activities of Daily Living Domain  Functional Communication Domain  Leadership Domain 

BASC3 Self Rating Scale Child (SRP-C)		
School Problems Composite Internalizing Problems Composite Inattention/Hyperactivity Composite Emotional Symptoms Index	Attitude to School Domain  Attitude to Teachers Domain  Locus of Control Domain  Social Stress Domain  Anxiety Domain  Depression Domain  Sense of Inadequacy Domain 	Atypicality Domain  Personal Adjustment Composite  Relations with Parents Domain  Interpersonal Relationships Domain  Self-Esteem Domain  Self-Reliance Domain 
BASC3 Self Rating Scale Adolescent (SRP-A)		
School Problems Composite Internalizing Problems Composite Inattention/Hyperactivity Composite Emotional Symptoms Index	Attitude to School Domain  Attitude to Teachers Domain  Sensation Seeking Domain  Locus of Control Domain  Social Stress Domain  Anxiety Domain  Depression Domain  Somatization Domain  Sense of Inadequacy Domain  Hyperactivity Domain  Attention Problems Domain 	Atypicality Domain  Personal Adjustment Composite  Relations with Parents Domain  Interpersonal Relationships Domain  Self-Esteem Domain  Self-Reliance Domain 
BASC3 Self Rating Scale College (SRP-COL)		
Internalizing Problems Composite Inattention/Hyperactivity Composite Emotional Symptoms Index	Locus of Control Domain  Social Stress Domain  Anxiety Domain  Depression Domain  Sense of Inadequacy Domain  Somatization Domain  Attention Problems Domain  Hyperactivity Domain  Sensation Seeking Domain  Alcohol Abuse Domain  School Maladjustment Domain 	Atypicality Domain  Personal Adjustment Composite  Relations with Parents Domain  Interpersonal Relationships Domain  Self-Esteem Domain  Self-Reliance Domain 
ABAS Parent 0-5 year old		
Conceptual Reasoning Domain Social Interactions Domain Practical Functioning Domain Adaptive Behavior Domain Score	Communication Skill Area Functional Pre-Academics Skill Area Self-Direction Skill Area Leisure Skill Area Social Skill Area Community Use Skill Area Home Living Skill Area Health and Safety Skill Area Self-Care Skill Area Motor Skill Area	
ABAS Parent 5-21 year old		
Conceptual Reasoning Domain Social Interactions Domain Practical Functioning Domain Adaptive Behavior Domain Score	Communication Skill Area Functional Academics Skill Area Self-Direction Skill Area Leisure Skill Area Social Skill Area Community Use Skill Area Home Living Skill Area Health and Safety Skill Area Self-Care Skill Area	

ABAS Adult 16-89 year old		
Conceptual Reasoning Domain Social Interactions Domain Practical Functioning Domain Adaptive Behavior Domain Score	Communication Skill Area Functional Academics Skill Area Self-Direction Skill Area Leisure Skill Area Social Skill Area Community Use Skill Area Home Living Skill Area Health and Safety Skill Area Self-Care Skill Area	
Detection Identification Attention Domain Composite	Pediatrics 4-5 year old	
Detection Identification One Back (speed) One Back (accuracy) Attention Domain Composite	Pediatric 6-9 year old	
Detection Identification One Back (speed) One Back (accuracy) Attention Domain Composite	Adult 10-21 year old	

[1] Higher scores indicate better performance (multiplicand = +1).

[2] Lower scores indicate better performance (multiplicand = -1).

### 10.5. Other Outcome Measures

The following composite scores will be computed and analyzed:

- Attention Domain Composite
  - o Peds Age 4-5: DET, IDN speed scores must exist
  - o Peds Age 6-9: DET, IDN, ONB speed scores; at least two of three scores must exist
  - o Ages 10-21: DET, IDN, ONB speed scores; at least two of three scores must exist

The composite scores will be calculated by:

- 1) Standardizing each of the test scores included in the cognitive domains against age-matched US normative population (international normative population for [redacted] computerized tests) data for that test (Section 10.6.1 specifies the procedure for the standardization of the tests for the purposes of creating the Attention Domain Composite score).
- 2) Computing the average of the available standardized test scores if the required number of scores available is met (as described above).

The Attention Domain Composite score is normalized based on age and therefore serves as the age-adjusted z-score in summary tables without any further calculations.

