## 10.6. Derived Variables

### 10.6.1. Standardized Scores: Comparison of Individual Scores to Age-Matched Normative Data for [REDACTED] Computerized Cognitive Tests (Age-Adjusted Z-Scores)

A comparison of individual scores to age-matched normative data will also be conducted. The process will be as follows:

- Performance on each neurocognitive outcome measure will be standardized relative to age-matched normative data (i.e., the score will be converted to a z-score by subtracting the age matched mean from the normative sample and dividing by the age-matched standard deviation (SD) from the same normative sample)
- The multiplicand equals 1 for outcome measures for which a higher score is indicative of better cognitive performance and -1 for outcome measures where a lower score is indicative of better cognitive performance. Please see Table 2 for details regarding the multiplicand for each outcome measure.
- The z-score will be calculated as follows:

$$z - Score (z_{ijt}) = \frac{(x_{ijt} - \bar{x}_t)}{SD_t} * Multiplicand$$

Where:

$t$  = is the outcome measure indicator

$i$  = indexes subject  $i$

$j$  = indexes the  $j$ th assessment for subject  $i$

$x$  = cognitive score

$\bar{x}_t$  = mean performance score of the age-matched normative sample for outcome measure  $t$

$SD_t$  = Standard Deviation of the age-matched normative sample for outcome measure  $t$

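### SAP 10.5 reports the plain mean of two or three test z-scores as an age-adjusted z-score, although its normative SD is below 1 and depends on which tests are averaged

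*SAP*

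**What the plan says.** SAP 10.5 sets the number of speed scores that enter the Attention Domain Composite by age:

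- ages 4-5: "Peds Age 4-5: DET, IDN speed scores must exist"
- ages 6-9: "Peds Age 6-9: DET, IDN, ONB speed scores; at least two of three scores must exist"
- ages 10 and over: "Ages 10-21: DET, IDN, ONB speed scores; at least two of three scores must exist"

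Each score is first standardised against age norms, which under SAP 10.6.1 means subtracting the age mean and "dividing by the age-matched standard deviation (SD) from the same normative sample". The composite is then obtained by "Computing the average of the available standardized test scores if the required number of scores available is met". The section closes by stating that the result is already normalised for age and "serves as the age-adjusted z-score in summary tables without any further calculations".

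Tables 3-6 of the SAP give age-specific norms for Detection, Identification, One Back speed and One Back accuracy. They give none for the composite. SAP Table 2 nevertheless lists the composite as a primary outcome measure of the computerised battery, beside the single tests. SAP 12.2 tabulates and lists age-adjusted z-scores, and their changes from the prior and the initial assessment, for every outcome measure.

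**The concern.** Centring each component at its age mean makes the composite's normative mean zero. It does not make the composite's SD equal to 1. Protocol 16.5 explains a Z-score as a distance from the mean counted in standard deviations, and SAP 10.6.1 divides each outcome measure by that measure's own age-matched SD. The composite is an outcome measure that gets no such division. It will stand in the same tables as scores that do have unit normative SD, including composites such as Full-Scale IQ, which SAP Table 7 rescales by its own SD.

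Two consequences follow on the age-adjusted scale. A given composite value is rarer in the norm population than its label implies. The scale also depends on the test set, which will change within children. Boys enter before age 6 (Protocol 6.2), the battery is repeated about every six months (SAP 8.2), and One Back is added at age 6 (SAP 10.4). From age 6 a test that fails its completion criterion is removed (SAP 9.4 and 11.1), which can take a child from three tests back to two. The assessments exist because of a theoretical safety concern about long-term PEG exposure (Protocol 3.4), so the scale on which an abnormal score is read should be the one the label states.

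**Working it through.** The documents give no SD for the composite, so there is no planned figure to reproduce.

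**Inputs.** The number of tests k is 2 at ages 4-5 and 2 or 3 from age 6 (SAP 10.5). Each component has normative SD 1 by construction (SAP 10.6.1). The correlation r between tests is not stated. I assume a common r of 0.3 to 0.7 and normal scores.

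**Formulas.** SD of the mean = sqrt((1 + (k-1)r)/k). Correctly scaled z = composite / SD. Share of the norm population below -1 = Phi(-1/SD).

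For example, at r = 0.5: k = 2 gives sqrt(1.5/2) = 0.866, and k = 3 gives sqrt(2/3) = 0.816.

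| r | SD, k=2 | SD, k=3 | Reported -1.00 is really (k=2 / k=3) | Share below -1 (k=2 / k=3) |
|---|---|---|---|---|
| 0.3 | 0.806 | 0.730 | -1.24 / -1.37 | 10.7% / 8.5% |
| 0.5 | 0.866 | 0.816 | -1.15 / -1.22 | 12.4% / 11.0% |
| 0.7 | 0.922 | 0.894 | -1.08 / -1.12 | 13.9% / 13.2% |
| True z-score | 1 | 1 | -1.00 | 15.9% |

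The limits are 0.707 and 0.577 at r = 0, and 1 for both only at r = 1. At or below -2 with r = 0.5, the shares are 1.05% and 0.72%, against 2.28%. A simulation with the SAP norms (1,000,000 draws per case, r = 0.5) gave SDs of 0.865 at age 5 with two tests and 0.816 at age 7 with three. Each single-test SD was about 1.00.

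**What is and is not distorted.** Take a child exactly one SD slow on every test. At age 5 the scores are 2.77951 + 0.11345 = 2.89296 (Detection) and 2.94433 + 0.11321 = 3.05754 (Identification). At age 7, with One Back speed added, they are 2.66173 + 0.09901 = 2.76074, 2.87557 + 0.07695 = 2.95252 and 3.07410 + 0.11496 = 3.18906. Each component z is -1, so the composite is -1.00 at both ages. The average component deficit is therefore reported correctly. What the label misstates is rarity: at r = 0.5 that composite marks the lowest 12.4% or 11.0%, not the lowest 15.9%.

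**Change of test set.** A child who stays at the 5th percentile of the composite (-1.645 SD) scores -1.645 x 0.866 = -1.42 with two tests and -1.645 x 0.816 = -1.34 with three. The apparent gain is about 0.08 at r = 0.5, and about 0.12 at r = 0.3. The direction depends on equal correlations. If Detection and Identification correlate 0.2 and each correlates 0.6 with One Back (again an assumption), that pair has SD sqrt(1.2/2) = 0.775 and the triple sqrt((3 + 2 x 1.4)/9) = 0.803, so the score would move the other way.

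**eTHINK scale.** SAP 10.6.3 divides by the eTHINK SD of the same outcome measure, which absorbs most of the shrinkage. Suppose 25% of the eTHINK reference has k = 2, at r = 0.5. The pooled SD is sqrt(0.25 x 0.750 + 0.75 x 0.667) = 0.829. The resulting SDs are 0.866/0.829 = 1.044 for two tests and 0.816/0.829 = 0.985 for three. With 10% at k = 2 they are 1.054 and 0.994.

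**The case against.** The strongest reply is that the scale used for judgement is not this one. Protocol 16 makes the eTHINK reference primary and general-population norms secondary. SAP 10.3 applies its 1 SD rule to the eTHINK mean and SD of composite scores, and SAP 10.6.3 rescales by the eTHINK SD. This stands, and it limits the point to the age-adjusted output. A reader might infer that the haemophilia-adjusted z-score and the expert-panel rule are mis-scaled too. The documents do not support that beyond a small residue where ages or test sets are pooled. Pooling over age is stated only in SAP 10.3. SAP 10.6.3 promises tables like Tables 3-6, which are by year of age, although its formula carries no age index.

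A second reply is that no deficit is hidden. The mean is unbiased on the component scale, the shrinkage applies equally to high scores, and the single tests are themselves primary outcomes that are standardised, tabulated, plotted and listed. This also stands. A reader might infer that the plan systematically conceals harm, but it only understates how unusual a composite is against the norm, in both directions.

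Third, no planned step counts children below -1 on the age-adjusted composite. The summaries are descriptive and print the observed SD. That lowers the stakes. It does not rescue the label, because an observed SD in trial patients does not tell the reader what the normative SD is.

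Finally, the sizes rest on assumed and equal correlations. That is true of the sizes and of the direction of a two-to-three-test shift. It is not true of the SD being below 1, which holds for any set of tests that are not perfectly correlated.

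**Conclusion.** The point holds for the age-adjusted Attention Domain Composite in the tables, listings and change scores of SAP 12.2. The plan calls a mean of z-scores a z-score and expressly rules out the rescaling step that would make it one. This conflicts with Protocol 16.5 and with the per-outcome SD rule in SAP 10.6.1.

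Under a common correlation of 0.3 to 0.7, the scale is too narrow by about 8-19% with two tests and 11-27% with three (1 minus the SDs above). That range is an assumption, because the documents give no correlations. Shifts within a child when the test set changes are about 0.1 z-unit at the 5th percentile for r of 0.3 to 0.5. They are smaller at higher r, and their sign depends on the correlation pattern.

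The error concerns the interpretation of a secondary, descriptive comparison. It changes no test, and the decision rule in SAP 10.3 is at most slightly affected. It is still worth correcting, because the plan as written would be programmed exactly as it stands.

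**What to change.** In SAP 10.5, after averaging, divide by the normative SD of the mean of the same tests at the same age, and only then call the result the age-adjusted z-score. The SD can come directly from the test vendor's normative data. It can also come from the normative inter-test correlations through sqrt((1 + (k-1)r)/k), or through the full correlation matrix if the correlations differ. Each combination of tests (two or three) needs its own divisor. Building the eTHINK reference from composites scaled the same way would remove the small residue there.

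If the normative data cannot be obtained, change the label to mean of z-scores, report the number of tests behind each value, and flag every change score in which the two assessments used different tests.

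The cost is one formula and a request for composite norms or correlations. SAP 10.6.1.1 shows only means and SDs by age, so it should not be assumed that the correlations are already held. The fallback needs no new data. Neither option needs new assessments of patients.
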